1.0 SAP Revision History

Protocol Version	Updated SAP version number	Section number changed	Description of and reason for change	Date changed	Timing of revisions relative to interim analysis
4	Not applicable				Post

2.0 INTRODUCTION

2.1 Background and rationale

Survivors of critical illness are at risk of developing physical dysfunction lasting from 5 to 8 years post-intensive care unit (ICU) discharge.[1, 2] Physical rehabilitation started in the ICU can improve patients' functional outcomes at hospital discharge.[3, 4] In a randomized trial, critically ill patients randomized to in-bed cycling started 2 weeks after ICU admission had farther 6-minute walk distance at hospital discharge compared to those receiving routine physiotherapy alone.[3] While in-bed cycling started earlier in a patient's ICU stay is safe [5-7] and feasible [8], the efficacy of early cycling on patients' function is unknown. A randomized trial comparing early in-bed cycling in addition to routine physiotherapy versus routine physiotherapy alone was therefore needed. We report this document according to the guidelines for the content of statistical analysis plans in clinical trials.[9]

2.2 Objectives

The primary objective of this trial is to determine the efficacy of early in-bed cycling (started within 4 days of mechanical ventilation initiation) and routine physiotherapy versus routine physiotherapy alone on patients' physical function 3 days post-ICU discharge.

3.0 STUDY METHODS

3.1 Trial design

CYCLE (Critical care cycling to improve lower extremity strength) is a 360-patient, international, multi-center, open-label, parallel group randomized trial (1:1 ratio) with blinded primary outcome assessment at 3 days post ICU discharge. Assessors were blinded to treatment group allocation.

3.2 Randomization

Randomization occurred after informed consent was obtained. We concealed allocation and used a central randomization process. We used a web-based, secure randomization service (<http://www.randomize.net/>). After informed consent, the site research coordinator logged in to the website, registered the patient, and received the randomized assignment, ensuring allocation concealment. Patients were stratified by center and age (≥ 65 vs. < 65 years old).

Interventions and comparator

Intervention (Cycling): Patients were randomized to receive 30 minutes/ day of in-bed cycling in addition to routine physiotherapy interventions, 5 days per week, during their ICU stay. Cycling occurred for a maximum of 28 days or stopped when the patient could march on the spot for 2 consecutive days, whichever occurred first.

Comparator (Routine): Patients received routine physiotherapy interventions per current institutional practice. Routine PT included, based on the patient's alertness and medical stability, activities to maintain or increase limb range of motion and strength, in- and out-of-bed mobility, ambulation, and assistance with optimizing airway clearance and respiratory function.[4, 10-12]

3.3 Sample size

Sample size and power

Our sample size of 360 patients was based on identifying a 1.0 point mean difference[13] between the Cycling and Routine groups for the Physical Function Test for ICU-scored (PFIT-s) measured at 3 days after ICU discharge.[14, 15] Psychometric studies of the PFIT-s identified the minimal clinically important difference was 1.0 points.[14, 16] Logistic regression analysis of patients enrolled in TryCYCLE [7] and the CYCLE pilot randomized study [8] identified that each 1.0 point increase in PFIT-s at ICU discharge (representing better function) was associated with a 40% reduction in the composite outcome of death, readmission to ICU, or requiring paid assistance for activities of daily living at hospital discharge.[13] Based on a standard deviation of 2.5 points at ICU discharge,[7, 17] a 1.0 point difference between groups,[13, 14, 16] and 90% power (0.05 alpha), we need to randomize and analyze 266 patients (133 per group). Based on 66 patients enrolled in the CYCLE Pilot RCT, we anticipated approximately 35% total attrition (25% ICU mortality, 1% mortality in the first 3 days post-ICU discharge, 5% missed primary outcome assessments at 3 days post-ICU, and 5% unblinded). Therefore, we will recruit 360 patients overall.

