4.3 Analysis populations

We will include all eligible randomized patients (i.e., excluding post-randomization exclusions representing non-eligible patients), according to the treatment they were randomized to receive. The analyses of our primary outcome will only include patients who survived to 3 days post-ICU discharge, as specified in our original protocol and sample size calculation.[21] The analysis of the PFIT-s at other timepoints (ICU awakening, ICU discharge, and hospital discharge) and all performance-based (strength and function) and patient-reported (e.g., quality-of-life) outcomes will only include patients who survive to the given timepoint. The analysis of hospital discharge location will only include those discharged from the hospital alive. The analysis of ICU and hospital mortality and length of stay, as well as duration of mechanical ventilation, will include all enrolled patients.

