6.2 Analysis methods

Statistical analysis

We will analyze patients according to the group to which they were randomized for all outcomes and will use multiple imputation to handle missing data (see section 6.3). We will summarize

baseline characteristics by group reported as mean (SD) or median (first quartile, third quartile) for continuous variables and count (percent) for categorical variables. The criterion for statistical significance will be set at $\alpha=0.05$ for the Primary Outcome. P-values will be reported to 3 decimal places, with those less than 0.001 reported as $p<0.001$.

Analysis of the Primary outcome

To determine if there is a difference in PFIT-s score at 3 days after ICU discharge between the Cycling and Routine groups, we will conduct a linear regression, including randomization (Cycling vs. Routine) as an independent variable. We will adjust for age (≥ 65 years versus <65 years) and clinical site as these were used as stratification variables in the randomization. We will report the results of the regression as mean difference in PFIT-s with corresponding 95% confidence intervals (CIs) and p-values. We consider a 1-point difference in score clinically important.[14, 16] Although the goal was to have all outcome assessors remain blinded to treatment allocation, this was not always feasible. To maximize use of available data, we will include all PFIT-s measures at 3 days post-randomization, regardless of blinding status of the outcomes assessor and report the proportion of assessments performed by blinded assessors.

To account for incomplete component data in the PFIT-s at 3 days post-ICU, we will concurrently consider data from the PFIT-s, 30s sit-to-stand, and 2-minute walk tests. We will evaluate all PFIT-s data components at 3-days post-ICU. We will identify all patients with any incomplete physical function data and review the scored values for all 4 components of the PFIT-s (i.e., shoulder flexion, knee extension, level of assistance required for the sit-to-stand, and step cadence). In the PFIT-s, a score of “0” represents a lack of physical ability to complete the outcome measure. Thus, if a patient attempted the item and was unsuccessful, the item receives a score of “0”, which is a true 0 (Table 4). See supplementary appendix for further details. Table 2 describes the primary outcome analysis.

Analysis of Secondary outcomes

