6.3 Missing data

To account for missing data in our performance-based and patient-reported outcomes, we will use multiple imputation for our analyses.[42-44] In the Cox proportional hazards analyses for ICU and hospital mortality outcomes, patients with incomplete follow-up will be censored at the time of last contact.

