6.4 Additional analyses

Subgroup analyses

We will perform three exploratory *a priori* subgroup analyses to investigate potential treatment effect modification for the primary outcome. All subgroup analyses will be adjusted for age and center.

- i. Age ≥ 65 versus < 65 years.
- ii. Baseline Clinical Frailty ≥ 5 versus < 5 .
- iii. Male versus female.

In separate linear regression models for each of the three subgroup analyses, we will include randomized treatment allocation, the subgroup variable, and the interaction between the subgroup variable and randomized treatment allocation as independent variables. These analyses will be adjusted for age and center. We hypothesize that the treatment effect will be greater for older compared to younger patients [45], greater in patients with frailty compared to those without [45], and greater in males compared to females [46, 47]. For statistical significance in the subgroup analyses, we will use an alpha of 0.10 for the interaction term. We will assess the credibility of any statistically significant subgroup effect using the method of Schandelmaier *et al.*[48] We will report these data in a forest plot.

Sensitivity analyses

To assess the robustness of our findings, we will conduct five sensitivity analyses for our primary outcome. All sensitivity analyses will be adjusted for age and center, unless specified.

- i. To account for ICU mortality on the primary outcome, we will conduct an analysis where we include all patients who died prior to 3-days post-ICU discharge and will assign a PFIT-s score of 0 for those patients.
- ii. We will conduct a linear regression analysis that includes only PFIT-s assessments performed by assessors blinded to treatment allocation.
- iii. We will conduct an analysis where we only include patients with adherence to the protocol on $\geq 80\%$ of planned ICU days. Adherence is defined as either received the randomized intervention or had a temporary exemption.
- iv. We will investigate the effect of missing data by conducting a complete case analysis, including only those patients with a total PFIT-s score at 3 days post ICU discharge.
- v. To determine if the cycling effect is affected by centre, we will conduct analysis adjusting for age only.

See Table 2 for further details.

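### SAP section 3.3: recruiting 360 does not deliver 266 analysed patients after 35% attrition; 234 remain (about 86% power), and the analysis now planned expects 248 to 254 observed outcomes (about 88% to 89%)

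*SAP*

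**What the plan says.** Section 3.3 assumes an SD of 2.5 points, "a 1.0 point difference between groups", 90% power and alpha 0.05, and concludes "we need to randomize and analyze 266 patients (133 per group"). On losses it says "we anticipated approximately 35% total attrition (25% ICU mortality, 1% mortality in the first 3 days post-ICU discharge, 5% missed primary outcome assessments", and adds 5% unblinded. The next sentence is the conclusion: "Therefore, we will recruit 360 patients overall".

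Three other sections decide which of these losses apply to the primary analysis:

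- Section 4.3 removes deaths. The primary analysis "will only include patients who survived to 3 days post-ICU discharge, as specified in our original protocol and sample size calculation".
- Section 6.2 keeps unblinded assessments. PFIT-s scores are used "regardless of blinding status of the outcomes assessor and report the proportion of assessments performed by blinded assessors".
- Section 6.3 imputes missed assessments: "To account for missing data in our performance-based and patient-reported outcomes, we will use multiple imputation for our analyses".

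Unblinding remains a loss only in sensitivity analysis ii of section 6.4, which "includes only PFIT-s assessments performed by assessors blinded to treatment allocation".

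**The concern.** Section 3.3 offers 360 as the consequence of 266 and about 35% attrition, but those two figures do not produce it. To allow for a loss fraction d, the required number is divided by (1 − d). The stated target instead matches the required number multiplied by (1 + d), which always recruits too few.

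Section 3.3 also no longer describes the planned analysis. It counts unblinded assessments as lost, whereas section 6.2 uses them.

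What is at stake is the 90% power figure. If the trial shows no difference, readers will use that figure to judge whether a 1.0-point effect was adequately tested. Section 4.3 also cites the sample size calculation in support of the survivor population, so the calculation should be coherent. The treatment estimate and its test are not affected.

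**Working it through.** **Inputs.** Difference 1.0, SD 2.5, power 90%, alpha 0.05 and the four loss components (25%, 1%, 5%, 5%) come from section 3.3. Two-sided testing comes from section 4.1 and 1:1 allocation from section 3.1. Power is for an unadjusted two-sample t-test (noncentral t).

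**Step 1: reproduce 266.** The standardised difference is 1.0/2.5 = 0.4. The noncentral t calculation gives 132.3 per group, rounded up to 133, or 266 in total, with power 90.15%. The stated 266 is correct.

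**Step 2: from 266 to 360.**

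- Dividing by the retained fraction: 266/(1 − 0.35) = 409.2, so 410.
- Multiplying by one plus the loss: 266 × 1.35 = 359.1, so 360.
- Deaths as the only loss: 266/(1 − 0.26) = 359.5, so 360.
- Largest loss that keeps 266 of 360: 1 − 266/360 = 26.1%.

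The SAP shows no formula, so the second and third routes both fit the target. Neither is a correct allowance for 35% total attrition.

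**Step 3: what 360 delivers.** The listed components add to 25 + 1 + 5 + 5 = 36%, which the word approximately covers. Added losses and losses applied in sequence are both shown.

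| Losses counted | Calculation | Observed | Power | Difference with 90% power |
|---|---|---|---|---|
| Section 3.3 as written, 35% | 360 × 0.65 | 234 | 86.1% | 1.06 |
| All four, in sequence (33%) | 360 × 0.75 × 0.99 × 0.95 × 0.95 | 241 | 87.1% | 1.05 |
| Deaths and missed assessments, added (31%) | 360 × 0.69 | 248 | 88.0% | 1.03 |
| Deaths and missed assessments, in sequence (29.5%) | 360 × 0.75 × 0.99 × 0.95 | 254 | 88.8% | 1.02 |
| Deaths only (26%) | 360 × 0.74 | 266 | 90.1% | 1.00 |

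The third and fourth rows correspond to the primary analysis now planned. About 266 survivors enter the model, but only 248 to 254 of them are expected to have an observed score. These rows credit imputation with no information beyond the observed scores.

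The blinded-only sensitivity analysis keeps all four losses. It has about 230 (36% added) to 241 (in sequence) observations, with power of 85.6% to 87.1%.

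**Step 4: could covariate adjustment close the gap?** The SAP gives no R-squared for age and site. If adjustment reduces the residual variance by a factor (1 − R²), and the degrees of freedom spent on sites are ignored, 90% power returns at R² of about 4% with 254 observed, 6% with 248 and 12% with 234.

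**The case against.** The strongest reply is that 86% describes no primary analysis this SAP plans. Unblinded assessments are now kept, so the relevant figure is 88% to 89%, within about 2 points of target. That is correct, and it limits the weight of the point.

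Even 88% to 89% is approximate. It comes from an unadjusted test on observed scores, whereas the plan is a regression adjusted for age and site with multiple imputation. PFIT-s is also measured at ICU awakening, ICU discharge and hospital discharge, so imputation may recover some information. Supplement 2 scores some incomplete components from observed function, though it cannot rescue a wholly missed assessment. True power could be at, above or below 90%. This stands, and it is why the figures should be labelled as approximate.

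The inputs are also uncertain by more than the gap. The SD is taken at ICU discharge, not at day 3. An SD of 2.42 with 248 observed, or 2.45 with 254, would give 90%, while an SD of 2.6 with the full 266 would give 87.8%. The attrition forecast rests on 66 pilot patients. This too is fair, but uncertain inputs do not excuse a derivation that fails on its own inputs.

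Finally, 360 is consistent with deaths as the only loss, and section 4.3 ties the survivor population to the sample size calculation. Section 3.3 does not say this. It names missed and unblinded assessments as attrition and derives 360 from the total. If deaths only was meant, the text misstates its basis and still needs correcting.

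**Conclusion.** The point holds. The 266 is right, but 360 does not follow from it with about 35% attrition, and no reading that counts all four stated losses leaves 266 patients.

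Taken as written, section 3.3 gives 234 analysed patients and about 86% power, a planned type II error of about 14% instead of 10%. For the primary analysis now planned, the shortfall is 1 to 2 points: about 88% to 89% power, or a type II error of about 11% to 12%. Both figures assume SD 2.5, the pilot-based loss rates, an unadjusted t-test, and no information gained from imputation or covariates.

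This is a modest error in a core design statement. It should be corrected, but it does not threaten the validity of the trial.

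**What to change.** Keep the attrition forecast in section 3.3 as the historical planning assumption, and add one note beneath it along these lines:

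> With 360 randomised and 35% attrition, about 234 patients would be analysed, giving about 86% power for a 1.0-point difference (90% power for about 1.06 points). Under sections 4.3, 6.2 and 6.3, unblinded assessments are not losses and missed assessments are imputed. About 266 survivors are therefore expected in the primary model, of whom about 248 to 254 should have an observed PFIT-s. Approximate power is 88% to 89% (unadjusted t-test, SD 2.5; no allowance for covariate adjustment or for information gained from imputation).

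The note should also say that it replaces the unqualified 90% statement, so that section 3.3 does not carry competing power figures. If the sponsor's records show how 360 was reached, one clause saying so would settle whether the deaths-only route was intended.

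The cost is a short addition to the text and a slightly less favourable power figure. Enrolment, population, model, test and alpha stay as they are.

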3.4 Framework

This trial was based on a superiority trial hypothesis that patients receiving in-bed cycling and routine physiotherapy early in their ICU stay will have better physical function at 3 days post-ICU discharge than those receiving routine physiotherapy alone.

3.5 Statistical interim analysis and stopping guidance

We conducted one blinded interim analysis that included the first 180 patients enrolled (half of our sample size) to assess for benefit and harm (serious adverse events). We used conservative statistical guidelines for data monitoring based on the modified Haybittle-Peto rule.[18] To maintain the overall type-I error rate (i.e., α), we evaluated the primary endpoint using a fixed simple conservative $\alpha=0.001$ for the interim analyses and $\alpha=0.05$ for the final analysis. The Data Monitoring Committee (DMC) recommended continuation of the trial on September 29, 2020.

3.6 Timing of final analysis

The first publication of the trial results will be prepared for the Cycling vs. Routine groups when every patient has reached 90 days post-randomization, and data for vital status at hospital discharge have been received. Longer-term endpoints for the economic evaluation will be reported in a separate publication.

In this document, we will outline only the analyses that will be included in the primary CYCLE manuscript.

3.7 Timing of outcome assessments

Supplement Table 1 outlines the schedule of study procedures with five timepoints for outcome assessments. The ICU Awakening timepoint was based on the physiotherapist's assessment of the patient's ability to consistently follow 5 verbal commands[19]. The ICU discharge timepoint occurred when the patient was discharged from the ICU or when a discharge order was written for the patient, whichever occurred first. The 3-day post-ICU timepoint occurred 3 days following the patient's physical discharge from the ICU. The hospital discharge timepoint occurred when a discharge order was written for the patient for the index admission (including alternative level of care). The 90-day timepoint occurred at 90 days following randomization.

4.0 STATISTICAL PRINCIPLES

4.1 Confidence intervals and P values

All statistical tests will be 2-sided and will be performed using a 5% significance level. We will report the two-sided 95% confidence intervals.

4.2 Adherence and protocol deviations

4.2.1 Adherence

Definitions:

“*Study days*” included all days in ICU from day of randomization up to 28 days post-randomization.

We did not plan for the randomized intervention to occur in the following circumstances:

- On days when a patient was randomized after normal physiotherapist working hours
- On days when a patient was transferred out of ICU before 12:00 pm
- On weekend days or statutory holidays
- For those randomized to in-bed cycling, patients who had marched on the spot for 2 consecutive days (and continued marching or higher mobility for the remainder of their ICU stay)

The remaining days were “*Planned intervention days*”. On weekdays (i.e., Monday through Friday), physiotherapists reviewed study patients for one or more of the following “Temporary exemptions” before offering the randomized intervention:

1. Increase in vasopressor/ inotrope within last 2 hours
2. Active myocardial ischemia, or unstable/ uncontrolled arrhythmia per ICU team
3. Mean arterial pressure <60 or >110 mmHg or per treating team within the last 2 hours
4. Heart Rate <40 or >140 bpm within the last 2 hours
5. Persistent SpO₂ <88% or per treating team within the last 2 hours

6. Neuromuscular blocker within last 4 hours
7. Severe agitation (Richmond Agitation and Sedation Scale >2 [or equivalent][20]) within last 2 hours
8. Uncontrolled pain
9. Change in goals to palliative care
10. Team perception that in-bed cycling or therapy is not appropriate for other new reasons (e.g., acute peritonitis, new incision/wound, known/suspected rhabdomyolysis)

If the patient had no “*Temporary exemptions*”, we offered the randomized intervention.

Each “Planned intervention day” without a “Temporary exemption” was an “*Eligible day*”. An eligible day where a patient did not receive the randomized intervention, was a “*Missed opportunity*”. Missed opportunities may have occurred due to:

1. Patient factors (e.g., patient not available due to a test, or declined)
2. Therapist factors (e.g., therapist not available due to vacation or sickness)
3. Equipment factors for patients in the Cycling arm (e.g., cycle ergometer malfunction)

Therefore, we define percent adherence whereby the numerator includes days in which patients received the randomized intervention or had a Temporary exemption and the denominator includes all planned intervention days (patients received the randomized intervention, Temporary exemptions, and Missed opportunities). We will report descriptive statistics on the percent protocol fidelity for the cohort by randomization group.

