v.	To determine if the cycling effect is affected by centre, we will conduct analysis adjusting for age only.	Excluding adjustment for clinical site will not change the estimated effect of cycling on the primary outcome.
		Linear regression, adjusted for age and clinical site. Only patients with blinded PFIT-s assessments will be included.
		Linear regression, adjusted for age and clinical site. Only patients who received the randomized intervention or had a temporary exemption on $\geq 80\%$ of planned intervention days will be included.
		Linear regression adjusted for age and clinical site. Only patients with a total score for the PFIT-s at 3 days post-ICU discharge will be included.
		Repeat the primary linear regression adjusted for age only (i.e., exclude clinical site)

Table 3: Description of Secondary outcome measures and analyses

Outcome	Description of Outcome	Measurement Timing	Analysis
Physical Function ICU Test [14, 15]	Patients complete 4 activities: arm strength, leg strength, ability to stand, and step cadences. Total scores range from 0 to 10 with higher scores representing better function.	ICU awakening, ICU discharge, hospital discharge	Includes survivors at each time point. Separate linear regressions for each timepoint, adjusted for age
Medical Research Council Sum Score [19, 49]	Standardized physical exam of 6 muscle groups (3 upper, 3 lower), using a 6-point scale (0=no contraction; 5= contraction sustained against maximal resistance), summed to a total score. Total scores range from 0 to 60 with higher scores representing more strength.	ICU awakening, ICU discharge, 3 days after ICU discharge, hospital discharge	Includes survivors at each time point. Separate linear regressions for each timepoint, adjusted for age
Medical Research Council Sum Score, categorized as <48 versus ≥ 48 [19, 49]	Standardized physical exam of 6 muscle groups (3 upper, 3 lower), using a 6-point scale (0=no contraction; 5= contraction sustained against maximal resistance), summed to a total score. Total scores range from 0 to 60 with higher scores representing more strength	ICU awakening, ICU discharge, 3 days after ICU discharge, hospital discharge	Includes survivors at each time point. Separate logistic regressions for each timepoint, adjusted for age

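### As worded, the marching rule in SAP Section 4.2.1 turns correctly uncycled days into Missed opportunities for Cycling patients who later regress

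*SAP*

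**What the plan says.** Section 3.2 gives the cycling arm up to 28 days of cycling, or less if cycling "stopped when the patient could march on the spot for 2 consecutive days, whichever occurred first". It does not require the marching to continue, and it gives no restart rule.

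Section 4.2.1 lists four circumstances in which the intervention was not planned. Three are defined by day, for example "On days when a patient was transferred out of ICU before 12:00 pm". The fourth is defined by patient: "For those randomized to in-bed cycling, patients who had marched on the spot for 2 consecutive days", with the added condition in parentheses "and continued marching or higher mobility for the remainder of their ICU stay".

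All other study days are Planned intervention days. A planned day without one of the ten Temporary exemptions is an Eligible day. "An eligible day where a patient did not receive the randomized intervention, was a" Missed opportunity. For percent adherence, days with the intervention or a Temporary exemption form the numerator, and "the denominator includes all planned intervention days", Missed opportunities among them.

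Sensitivity analysis iii in Section 6.4 will "only include patients with adherence to the protocol on" at least 80% of planned ICU days. Table 2 gives the same rule: patients treated or exempt on at least 80% "of planned intervention days will be included".

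**The concern.** The stopping rule and the adherence rule use different conditions. The stopping rule is met on the second consecutive marching day. The adherence rule also requires that mobility never drops again before the patient leaves the ICU, which is known only in retrospect. On the third marching day the physiotherapist follows Section 3.2 and does not cycle. If the patient regresses a week later, that correct decision is reclassified as non-adherence.

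Two outputs depend on this: the adherence reported by group, and the set of patients in sensitivity analysis iii. The marching bullet applies to the Cycling arm only, so the misclassification is confined to one arm. It is also triggered by a loss of mobility, which is related to the outcome, since step cadence is one of the four PFIT-s items. The direction of any resulting bias cannot be determined from the SAP.

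**Working it through.** The SAP states no figure that depends on this rule, so there is none to reproduce. The check has two parts.

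**Tracing the definitions.** Take a Cycling patient who marches on 2 consecutive days, is no longer cycled, keeps marching for some weekdays, and then regresses while still in the ICU.

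1. Section 3.2: the stopping rule was met, so not cycling on the later marching weekdays follows the plan.
2. Section 4.2.1, marching bullet: marching did not last to the end of the ICU stay, so the bullet does not apply to this patient.
3. The weekdays between the stop and the regression therefore stay Planned intervention days.
4. None of the ten Temporary exemptions mentions marching or having met the stopping rule. Item 10 (other new reasons why therapy is not appropriate) comes closest, but its examples are new clinical problems such as peritonitis, a wound or rhabdomyolysis, not improvement.
5. Without another exemption the days are Eligible days, and without cycling they are Missed opportunities. They enter the denominator and not the numerator.

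**Effect on the 80% cut-off.** All counts below are assumptions, because the SAP gives none. Let:

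- D = planned days delivered or exempt (numerator)
- m = uncycled marching weekdays after the second marching day and before the regression
- k = genuinely missed sessions

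As written, adherence = D/(D + k + m). It is below 0.80 when D < 0.8D + 0.8(k + m), that is, when k + m > D/4. If days are removed while marching lasts, adherence = D/(D + k).

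| D | k | m | As written | Marching days removed |
|---|---|---|---|---|
| 8 | 0 | 3 | 8/11 = 72.7% (out) | 8/8 = 100% (in) |
| 8 | 0 | 2 | 8/10 = 80.0% (in) | 8/8 = 100% (in) |
| 12 | 0 | 3 | 12/15 = 80.0% (in) | 12/12 = 100% (in) |
| 4 | 1 | 1 | 4/6 = 66.7% (out) | 4/5 = 80.0% (in) |
| 6 | 1 | 1 | 6/8 = 75.0% (out) | 6/7 = 85.7% (in) |
| 7 | 1 | 1 | 7/9 = 77.8% (out) | 7/8 = 87.5% (in) |
| 8 | 1 | 1 | 8/10 = 80.0% (in) | 8/9 = 88.9% (in) |

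The first row is, for example, 6 cycled weekdays, 3 marching weekdays without cycling, a regression, and 2 resumed weekdays. The third row is the same patient with 4 exempt days added, which brings adherence back to the cut-off.

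With k = 0, a single such day (m = 1) excludes nobody with D of 4 or more. With k = 1, a single such day excludes patients with D from 4 to 7.

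If the protocol's stop is permanent, the 2 weekdays after regression are also correctly uncycled. The first-row patient then has 6/11 = 54.5% as written, against 6/6 = 100% with the parenthesis deleted.

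**The case against.** The best defence is that the bullet was meant to work by day. Its lead-in describes when treatment was planned, and nobody can plan on the basis of a future regression. Section 4.2.1 also says the intervention was offered whenever no Temporary exemption applied. That sits badly with days that are planned and unexempted but on which cycling was rightly not offered. The listed causes of Missed opportunities (patient, therapist, equipment) do not resemble a stopping rule being met. On this view the parenthesis only makes days after a regression planned again. The Cycling-only scope is natural, since only that arm has a marching stop. The unseen protocol may also settle whether cycling resumes.

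Much of this stands as an account of intent. It does not change the text: the condition runs to the end of the ICU stay, not for as long as marching lasts, and a program written from it would apply it that way. The sentence about offering the intervention shows the adherence rule at odds with the stopping rule; it does not repair it. Whether cycling resumes after regression affects only the later days. The marching days before it are correctly uncycled either way.

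The objection is right about size. The counts are assumed, several assumed cases leave the patient in, and the analysis affected already selects on adherence after randomization.

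**Conclusion.** The point holds: as written, Section 4.2.1 counts correctly uncycled marching weekdays as Missed opportunities for any Cycling patient who later regresses in the ICU. It is minor. It affects the descriptive adherence figures for the Cycling arm and one of five sensitivity analyses. The primary analysis is unaffected. A patient wrongly leaves sensitivity analysis iii only if D/(D + k) is at least 80% and k + m exceeds D/4. The number of such patients is not given and is probably small. The conclusion assumes that the bullet is programmed as worded and that no other Temporary exemption covers the days in question.

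**What to change.** Reword the fourth bullet in Section 4.2.1 by day: in the Cycling arm, days after the second consecutive marching day are not planned intervention days for as long as marching or higher mobility continues. If the protocol resumes cycling on regression, add that days from the loss of marching are planned again. If the protocol's stop is permanent, delete the parenthesis instead. Derive both percent adherence and the sensitivity analysis iii set from the revised rule.

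The cost is one line of text and the matching line in the adherence derivation. The daily mobility data are already needed to apply the current bullet. Section 3.2 and the primary analysis need no change.
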